### 3.2.4 Last visit during the Exposure Period

The Last Visit for an assessment is the last non-missing assessment prior to or on the date of last dose of PSL (Section 3.2.2.1). All scheduled and unscheduled will be considered. Last Visit will be determined separately for each study assessment. Last Visit during the Exposure Period will be included in the by-visit summary unless noted otherwise. Similarly, the minimum and maximum values are defined as the minimum and maximum values prior to or on the date of last dose of PSL.

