**Table 3–3.21: Start and end of EP0093 analysis periods**

Description	Start	End	Details
Evaluation Period	Entry Visit (EV, Visit 1)	EOS or EDV or the last contact date if neither EOS or EDV visit is available.  At the time of a clinical cutoff prior to the study completion, if a subject is ongoing and doesn't have the EDV, the end of the period is set to the clinical cutoff date.	The Entry Visit (EV, Visit 1) will be done on the same day as the last visit of the parent study. Subjects will return to clinic every 2 weeks during Month 1, every month during Month 2-3, every 3 months after Month 3 up to Month 24.
Taper Period/ Safety Follow-Up Period	1 day after end date of evaluation period.	The date of final contact.  At the time of a clinical cutoff prior to the study completion, if a subject is ongoing, the end of the period is set to the clinical cutoff date.	Applies only to patients who discontinue the study or complete it without continuation of PSL treatment.
Exposure Period	Date of first dose of PSL	Date of last dose of PSL	Extends from the date of first dose until the last dose of PSL in EP0093. It may include the Evaluation and Taper Period. (Section 3.2.2.1).

At the time of a clinical cutoff prior to the study completion, subjects without the Study Termination eCRF will be classified as “ongoing.” Only the data on or prior to the clinical cutoff date will be included in the analyses.

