For hematology and blood chemistry parameters that are identified in Table 10-1, the shift from Baseline in category (relative to normal range: low, normal, high) to the maximum and minimal values during the exposure period will be presented. Categorical urinalysis results will be summarized by visit.

PCST criteria have been developed for the PSL program based on FDA Division of Neuropharmacologic Drug Products guidelines with some UCB-defined additions and are provided in Appendix 12.1. For lab parameters with treatment emergent PCST criteria, the number and percentage of subjects with a PCST will be summarized for the overall and by 3-month interval during the Exposure Period. Subject numbers for those meeting the PCST will also be presented. Results of additional tests like the urine pregnancy test will be listed.

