## 9.5 Vital signs, physical findings, and other observations related to safety

### 9.5.1 Vital signs

Vital measurements (including SBP, DBP, PR and RR) are taken at every scheduled visit. These measurements are generally collected in standard units. If any measurements are collected in international units, they will be converted to standard units for summaries. Subject Listings will be prepared for vitals variables including absolute change from Baseline and abnormality criteria flag.

The observed value and absolute change from Baseline will be summarized (SS) descriptively by scheduled study visit, as well as Last Visit, maximum value, and minimal value. Data collected at unscheduled visits will not be included in the by-visit summary.

The number and percentage of subjects with abnormal vital signs described in Appendix 13.2 will be summarized for the overall and by 3-month interval during the Exposure Period. Subject numbers for those meeting the abnormal criteria will also be presented.

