### 9.5.2 Electrocardiograms

The following ECG parameters will be recorded: heart rate, PR-interval, QRS-duration, QT-interval, QTcB [QT corrected for heart rate using Bazett's formula] or QTcF [QT corrected for heart rate using Fridericia's formula], and Investigator's conclusion on ECG profile.

The 12-Lead ECG results are collected at Entry Visit, Visit 3, Visit 5 and at visits every 6 months thereafter. An ECG at the SFU will be performed only if abnormal at EOS or EDV Visit.

For each ECG, the overall ECG result, is also collected, categorized by the investigator as one of: no abnormality, an abnormal but not clinically significant finding, or a clinically significant finding.

QTcB and QTcF will also be presented by following classification per visit:

- Observed results:  $<450\text{ms}$ ,  $450-<480\text{ms}$ ,  $480-<500\text{ms}$  and  $\geq 500\text{ms}$
- Change from Baseline:  $<30\text{ms}$ ,  $30-<60\text{ms}$ ,  $\geq 60\text{ms}$

The observed ECG parameter values and their absolute change from Baseline will be summarized (SS) descriptively for each scheduled assessment visit, as well as Last Visit, maximum value, and minimal value.

The number and percentage of subjects with no abnormality, an abnormal but not clinically significant finding, and a clinically significant finding will be summarized for each of the scheduled assessment visits. Percentages for the visit will be relative to the number of subjects with an ECG result for the visit.

The number and percentage of subjects with an abnormal ECG value described in Appendix 13.3 will be summarized for the overall and by 3-month interval during the Exposure Period. Subject numbers for those meeting the abnormal criteria will also be presented.

All 12-Lead ECG parameters will be listed per visit, including the change from baseline and a abnormality criteria flag. In addition, the data from patients with at least one finding will be listed with the finding.

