### 13.3 ELECTROCARDIOGRAM (ECG) – ABNORMAL

Abnormality criteria to be applied in the assessment of ECG parameter values are given below:

Parameter	Age	Abnormality Criteria
QT interval (ms)	1m-<12y	>500
	>12y	>500 or ≥60ms increase from Baseline
QTc(F) (ms)	<6m	>490, or >15% increase from Baseline
	6m-<3y	>440, or >15% increase from Baseline
	3y-<12y	>440, or >15% increase from Baseline
	>12y- <17y	>440, or >15% increase from Baseline
	≥17y	>500 or ≥60ms increase from Baseline
QTc(B) (ms)	<6m	>490, or >15% increase from Baseline
	6m-<3y	>450, or >15% increase from Baseline
	3m-<12y	>450, or >15% increase from Baseline
	>12y- <17y	>450, or >15% increase from Baseline
	≥17y	>500 or ≥60ms increase from Baseline
PR interval (ms)	<6m	>150, or >25% increase from Baseline
	6m-<3y	>170, or >25% increase from Baseline
	3y-<12y	>180, or >25% increase from Baseline
	>12y - <17y	>200, or >25% increase from Baseline
	≥17y	Treatment-emergent value >200, >220, >250
QRS interval (ms)	<6m	>90, or >25% increase from Baseline
	6m-<3y	>90, or >25% increase from Baseline
	3y-<12y	>100, or >25% increase from Baseline
	>12y - <17y	>110, or >25% increase from Baseline
	≥17y	Treatment-emergent value >100, >120, >140
Heart rate (bpm)	<6m	<100, >180
	6m-<3y	<90, >150
	3y-<12y	<60, >130
	>12y	<50, >120

Abbreviations: bpm = beats per minute; m = months; ms = milliseconds; QTc = corrected QT interval; y = years. A month is defined as 30 days; a year is defined as 365.25 days.

Note: Treatment-emergent is defined as meeting the criteria at any post-Baseline visit during EP0093 (including unscheduled visits) and not meeting the same criteria during Baseline in the parent study.

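### The SAP's laboratory, vital-sign and ECG abnormality counts and maximum/minimum values stop at the last PSL dose, an unrecorded departure from the protocol's reporting by period

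*SAP*

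**What the plan says.** **Window.** The analysis-periods table in SAP 3.2.3 says of the Exposure Period: "Extends from the date of first dose until the last dose of PSL in EP0093". No days are added after the last dose.

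**Extremes.** SAP 3.2.4 uses the same cut-off: "the minimum and maximum values are defined as the minimum and maximum values prior to or on the date of last dose of PSL". The laboratory shift tables in SAP 9.3 run from Baseline to those maximum and minimum values, so they stop there too.

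**Counts.**
- Laboratory (SAP 9.3): "the number and percentage of subjects with a PCST will be summarized for the overall and by 3-month interval during the Exposure Period".
- Vital signs (SAP 9.5.1): "abnormal vital signs described in Appendix 13.2 will be summarized for the overall and by 3-month interval during the Exposure Period".
- ECG (SAP 9.5.2): "abnormal ECG value described in Appendix 13.3 will be summarized for the overall and by 3-month interval during the Exposure Period".

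**Text that points the other way.** The note to SAP 13.3 defines a treatment-emergent ECG abnormality as "meeting the criteria at any post-Baseline visit during EP0093 (including unscheduled visits") and absent at the parent-study Baseline. Protocol 12.3 names the study periods as Evaluation, Taper and SFU, and plans laboratory, vital-sign and weight abnormalities to be tabulated by period as well as by visit. For ECG abnormalities it plans a listing by period and visit. SAP 3.9, which sets out changes to protocol-defined analyses, does not mention a move to an Exposure Period window.

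**The concern.** Long-term safety and tolerability is the primary objective, and these tables are where a reader looks for the incidence of abnormal values. The cut-off is not neutral. A subject who tapers attends the EDV while still taking PSL, so the EDV values count. A subject who stops without a taper and attends afterwards has EDV values that do not count. The protocol foresees untapered stops for safety reasons: certain liver criteria (Protocol 6.3.1), and pregnancy as one of two options (Protocol 9.1.7). Observation of people who stopped for safety could thus be less complete in these tables than that of people who tapered. Withdrawal effects are also something the protocol sets out to monitor (Protocol 9.3.8), yet the vital signs measured off drug enter none of the abnormality counts.

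**Working it through.** No figure in the plan bears on this, so the check applies the date rule to example visits and then traces where the excluded values go.

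**1. Rule.** A value enters the counts only if first-dose date ≤ assessment date ≤ last-dose date. For maximum and minimum, the upper limit is the same.

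**2. Example dates** (day numbers are illustrative).
- *Tapering subject*, EDV on Day 100. Note c to the schedule gives 3 weeks of taper plus 1 drug-free week: last dose 100 + 21 = Day 121; End of Taper 121 + 7 = Day 128; SFU 121 + 30 = Day 151. The EDV is counted (100 ≤ 121). End of Taper and SFU are not (128 and 151 > 121). Protocol 5.1 words the taper as 4 weeks; then last dose is Day 128, End of Taper Day 135 and SFU Day 158, with the same result.
- *Untapered stop*, last dose Day 100. An EDV on Day 100 is counted. An EDV on Day 101, 107 or 114 is not, nor is SFU on Day 130.

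**3. What is collected after last dose.**
- *Laboratory:* EDV samples if the EDV comes late, and PDILI follow-up chemistry, which Protocol Table 9-3 sets at least twice a week for most criteria. Nothing is scheduled at End of Taper or SFU.
- *ECG:* a late EDV recording. Under SAP 9.5.2 and note j to the schedule, an SFU ECG is taken only if the EOS or EDV tracing was abnormal, so it will rarely reveal a new abnormality. Protocol 8.3.1 lists the SFU ECG without that condition.
- *Vital signs:* a late EDV, plus End of Taper and SFU for every subject who stops PSL.

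**4. Where those values still appear.**
- SAP 3.2.3.1 assigns EDV safety data to a scheduled visit with no reference to last dose. They can then enter by-visit tables, including the QTc categories and the per-visit ECG classification. But by-visit tables include only visits at which the assessment is scheduled. No ECG is scheduled at Visits 2, 4, 6, 8 or 10, so, as worded, an EDV ECG assigned to one of those visits drops out. If it also came after last dose, it reaches no ECG summary.
- Potential Hy's Law is counted at any visit (SAP 9.4), but it needs transaminase and bilirubin elevation at the same visit. PDILI visits that cannot be mapped are listed only.
- End of Taper and SFU vital signs enter the by-visit observed and change summaries, but neither the abnormality counts nor the maximum and minimum rows. A visit row could therefore show a value beyond the stated study maximum.
- Listings carry the flags and show EDV and unscheduled visits, but give no incidence.

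**5. SAP 9.5.2 against 13.3.** Section 9.5.2 applies the appendix criteria within the Exposure Period; the appendix note applies them over the whole study. Among the adult criteria, only the PR and QRS rows use the term treatment-emergent, so the direct conflict lies there.

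**6. Size.** The documents give no proportion of untapered stops. Assume that 2% to 20% of 1000 subjects stop abruptly with a later EDV, and that 1% to 5% of these have a first abnormality there:
- low: 1000 × 0.02 × 0.01 = 0.2 subjects;
- high: 1000 × 0.20 × 0.05 = 10 subjects.

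This covers late EDVs only, not End of Taper or SFU vital signs. The base of 1000 is the planned number; SAP 3.9 refers to early termination and reduced enrolment, so the real base may be smaller.

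**The case against.** An on-treatment window is a legitimate choice. Pooling off-drug days into it would mix drug effect with withdrawal and with replacement therapy, and the documents give no pharmacokinetic reason for a particular residual window. Taper is the default, so the usual EDV precedes the last dose. TEAEs are not wholly free of the cut either: the overall tables are, but those by 3-month interval and by dose at onset use the Exposure Period (SAP 9.2). All of this stands, and it argues against simply stretching the on-treatment window to 30 days. It does not argue against a separate row.

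A reader might infer more than the text supports:
- *That post-dose findings are missing from every count.* They are not: by-visit tables, the any-visit Hy's Law count and the overall TEAE tables can hold them.
- *That a subject stopped for a liver criterion vanishes from the laboratory table.* The value that triggers the stop would normally fall on or before the last dose and be counted. What can be lost is a later peak or a new finding.
- *That SFU laboratory abnormalities are discarded.* None are scheduled.

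**Conclusion.** The point holds in limited form. The abnormality counts, the maximum and minimum values and the laboratory shifts end on the last-dose date. For laboratory values and vital signs this departs from Protocol 12.3 without being recorded in SAP 3.9. For adult PR and QRS it conflicts with the note to SAP 13.3. What falls outside is EDV data after an untapered stop, later PDILI peaks, and all End of Taper and SFU vital signs.

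The number of subjects affected is unknown and may be small; the range of 0.2 to 10 per 1000 rests entirely on assumed proportions. It would be tempting to say that 2% to 10% of 1000, that is 20 to 100 subjects, are missed. Those proportions are also assumed, and the result would count late EDVs, not missed abnormalities. Nor do the documents show that incidence is materially understated; they show only that the tables cannot reveal it if it is.

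**What to change.** 1. In SAP 9.3, 9.5.1 and 9.5.2, keep the on-treatment counts and the 3-month intervals. Add to each abnormality table one row for the time after last dose (day after last dose to final contact or SFU) and one overall row covering both.
2. State that unscheduled samples and central-laboratory PDILI samples are eligible for these rows.
3. In SAP 3.2.4, give maximum, minimum and the laboratory shifts also over the whole span from first dose to final contact. The Last Visit row can stay on treatment.
4. Align SAP 9.5.2 with the note to 13.3, so that one window governs the PR and QRS criteria.
5. Record in SAP 3.9 whatever departure from Protocol 12.3 remains.

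The cost is SAP wording, a date condition in programming and slightly more tabulation. No new data are needed. Off-drug findings must be labelled as such, so that they are not read as on-treatment incidence.

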### 3.2.5 Interval duration

A month is defined as 30 days and time intervals based on monthly durations are defined as a multiple of 30 days (eg, 12 months is defined as 360 days).

Interval Duration Definition:

- Months 0-3 Days 1-90
- Months >3-6 Days 91-180
- Months >6-9 Days 181-270
- Months >9-12 Days 271-360

Subsequent intervals are defined in a similar manner. For the analysis of seizure data during the Evaluation Period, 3-month intervals will be derived for the Evaluation Period. For the analysis of AEs and safety variables, 3-month intervals will be derived for the Exposure Period.

### 3.2.6 Number of completers by time interval

Each subject will be classified into one or more of the following intervals based on the duration of the Evaluation Period:

- $\geq 3$  months =  $\geq 90$  days
- $\geq 6$  months =  $\geq 180$  days
- $\geq 12$  months =  $\geq 360$  days
- $\geq 18$  months =  $\geq 540$  days
- $\geq 24$  months =  $\geq 720$  days

The duration of the Evaluation Period is calculated as the date of the end of the Evaluation Period – EV +1. Selected efficacy variables will be analyzed for completers by time intervals. The number of completers by time interval is also defined as completer cohort.

## 3.3 Definition of Baseline values

Baseline refers to the baseline of the parent study unless noted otherwise.

### **3.3.1 Baseline for variables based on seizure count**

The current study does not provide a baseline period. Baseline values for observable focal-onset seizures (Types IA1, IB, and IC) and for all Type I seizures will be derived from subject diary data collected during the 4-week Prospective Baseline Period of the parent studies.

[Definition from parent studies: The Baseline value will be the seizure frequency per 28 days prior to the day of the first dose of IMP and is defined as the number of seizures standardized to a 28-day baseline period. It is computed for each subject as the number of seizures recorded over the subject's baseline diary period, divided by the subject's total number of non-missing days in that period, multiplied by 28.]

### **3.3.2 Baseline for other variables**

Unless otherwise specified, Baseline values from the parent study will be used in the analysis which is defined as the last valid measurement before the first study medication administration, including the pre-dose assessments on the day of Visit 2. If a Baseline visit measurement is missing, and a Screening visit measurement is available, the most recent Screening value will be utilized. Both scheduled and unscheduled Screening visits will be considered.

If a scheduled Baseline assessment is taken on the same day as first administration of study medication and no time is collected, it will be assumed to have been taken prior to study medication. The time point used will be determined separately for each variable. An exception is blood pressure, where a complete set of both systolic and diastolic blood pressure should be selected for Baseline.

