12.3 Planned safety analyses

All safety variables will be analyzed by descriptive methods and listed on the SS.

Treatment-emergent AEs will be summarized by study period (Evaluation, Taper, and SFU) and reported for cumulative 3-month time intervals and categories of total duration of exposure, using the Medical Dictionary for Regulatory Activities (MedDRA[®]) primary System Organ Class (SOC) and Preferred Term in incidence tables. Separate tables will be provided for AEs leading to withdrawal from the study and SAEs overall and by the subcategories listed above.

Laboratory values, ECG data (heart rate, PR interval, QTcB, QTcF, and QRS interval), vital signs, and weight will be summarized by period and visit (actual values and change from Entry Visit). Possible clinically significant treatment-emergent abnormalities for laboratory values,

vital signs, and weight will be listed and summarized by period and visit. Electrocardiogram abnormalities will also be listed by period and visit.

Summary tables (and graphical outputs if needed) will be performed on the Doppler echocardiography data.

Physical and neurological examinations, psychiatric assessments and the withdrawal symptoms using the CIWA-B assessment will be provided as listing by period and visit (actual values and change from Entry Visit). The C-SSRS results will be displayed in a listing.

Any additional listings or tabulations will be described in the SAP.

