## 3.9 Changes to protocol-defined analyses

Due to the COVID-19 impact on site initiation and enrollment as well as early termination of the study, the following items in the protocol were updated in the SAP

Section in this SAP	Description	Change from the protocol
Table 2-1:	Schedule of Assessments	Added: Setting (Required Onsite) column to include data that may be collected through phone or video calls for visit, during the pandemic.

3.10	COVID-19 eCRF	Added, see section 3.10 for details
4.4	Examination of subgroups	Removed China as a region
10.2.1.8	Derivation of other efficacy variables	
Removed: Drug Loads of AEDs
 
Changes in drug load are captured by number of products and daily dose per given product recorded in the AED Medication CRF. Drug load will be assessed using ratio of actual daily dose and World Health Organization defined daily dose (DDD).  “https://www.whocc.no/atc_ddd_index/?code=N03A&showdescription=no”.
 
The daily dose of the administered AED will be calculated at Entry Visit, Visit 8, and EOS. All AEDs which has the stop date at the visit (EV, Visit 8, EOS) or ongoing and the start date prior to the visit will be considered administered at that specific visit.
 
The drug load of all AEDs will be calculated as the sum of ratios of dose and DDD for each of the AEDs at the respective visit. The drug load of each AED class will be calculated as the sum of ratios of dose and DDD for each of the AEDs within the AED class. AED classes included in this analysis are:
 
 
• SV2A: levetiracetam and brivaracetam
 
• BZD: ATC code N05BA
 
• sodium channel-blocking AED (SCB (+): carbamazepine, oxcarbazepine, eslicarbazepine, phenytoin and lamotrigine
 
 
Ratio of dose and DDD, absolute change from EV in the ratio, and percent change from EV in the ratio will be summarized by all AEDs, AED drug class and by each of the AEDs. For two visits, the absolute change of a given AED drug load can be calculated if the product is administered at one of the visits; and the percent change can only be calculated if the AED is administered at EV. The change in number of all AEDs at Visit 8 and EOS relative to EV will also be summarized.

11	COVID-19	The impact of COVID-19 global pandemic on this study is detailed in section 3.10. COVID-19 impact will be listed by

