### 9.2 Adverse events

Adverse events are recorded on the Adverse Event CRF as they occur, from the time informed consent is granted until study completion or study termination (end of the SFU period 30 days after the last IMP intake). Also, adverse events ongoing at the Entry Visit in EP0093 will be recorded in the Adverse Event\_Parent Study CRF.

A treatment-emergent adverse event (TEAE) is defined as any event not present prior to the initiation of the first dose of study treatment in this study or any unresolved event already present

before initiation of the first dose that worsens in intensity following exposure to the treatment. TEAEs are AEs with start dates on or after the date of first dose of PSL in EP0093. The number and percentage of subjects who experience TEAEs at any time during the study will be summarized (using the SS) by SOC and PT.

Unless noted otherwise, TEAEs during the study will be summarized. At the time of a clinical cutoff, TEAEs with onset date prior to or on the clinical cutoff date will be included. TEAEs are assigned into an analysis period or time interval based on the start date. Adverse event summaries will be ordered in terms of decreasing frequency for SOC, and PT within SOC. The following tabular summaries will be presented for the SS:

- Ongoing AEs at EP0093 study entry
- Incidence of TEAEs during the Study – Overview by Region
- Incidence of TEAEs by Region
- Incidence of TEAEs by 3-month time interval during the Exposure Period
- Incidence of Serious TEAEs
- Incidence of TEAEs by Relationship
- Incidence of SAEs by Relationship. Of note, this table is needed for data transparency reporting.
- Incidence of Fatal TEAEs by Relationship. Of note, this table is needed for data transparency reporting.
- Incidence of TEAEs by Maximum Intensity
- Incidence of TEAEs leading to discontinuation (ie, drop out)
- Incidence of TEAEs leading to dose reduction
- Incidence of TEAEs occurring in at least 5% of Subjects
- Incidence of TEAEs by Dose at Onset ( $\leq 200\text{mg/day}$ ,  $>200\text{mg/day}$  to  $\leq 400\text{mg/day}$ ,  $>400\text{mg/day}$  to  $\leq 600\text{mg/day}$ , and  $>600\text{mg/day}$ ) during the Exposure Period.
- Incidence of Non-Serious TEAEs above the Threshold of 5% of Subjects. This table is needed for data transparency reporting.

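### The SAP replaces the protocol's change from Entry Visit with change from the parent-study Baseline for safety measurements, does not list the departure, and leaves treatment-emergent with two reference points

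*SAP*

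**What the plan says.** Protocol 12.3 covers laboratory values, ECG data, vital signs and weight in one sentence. It ends: "vital signs, and weight will be summarized by period and visit (actual values and change from Entry Visit"). The same section plans flags, beginning "Possible clinically significant treatment-emergent abnormalities for laboratory values" and continuing to vital signs and weight, but names no reference visit for them. For ECG it says only "Electrocardiogram abnormalities will also be listed by period and visit".

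SAP 3.3 sets the general rule: "Baseline refers to the baseline of the parent study unless noted otherwise". SAP 3.3.2 repeats it for non-seizure variables: "Unless otherwise specified, Baseline values from the parent study will be used in the analysis". The value used is the last valid one before the first study medication in the parent study. SAP 9.3 (laboratory), 9.5.1 (vital signs) and 9.5.2 (ECG) then summarise change from Baseline by visit and note no exception.

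Emergence is defined in two ways. For adverse events, SAP 9.2 says "TEAEs are AEs with start dates on or after the date of first dose of PSL in EP0093". For ECG values, the note to SAP 13.3 requires the criterion to be met at a post-Baseline visit in EP0093 while "not meeting the same criteria during Baseline in the parent study".

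SAP 3.9 introduces its table with "the following items in the protocol were updated in the SAP". The rows cover COVID-19, removal of China as a region, AED drug load and the Japan addendum. The safety reference point is not among them.

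**The concern.** EP0093 is an extension, so time passes and treatment is given between parent Baseline and Entry. Change from parent Baseline mixes what happened in the parent study with what happened here. Change from Entry isolates EP0093. The protocol chose the second for its change summaries; the SAP supplies only the first and does not present this as a departure.

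Three things are at stake:

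- **The protocol-defined summaries are not produced.**
- **Some EP0093 flags can describe an earlier change.** A finding that arose in the parent study and has since been stable can appear as an EP0093 finding.
- **Emergence is inconsistent.** An ECG value may be labelled treatment-emergent in EP0093 while the matching adverse event, with onset before the first EP0093 dose and no later worsening, is not.

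**Working it through.** No sample size, power or error rate bears on this point, so the check compares definitions and then applies them to hypothetical values.

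**1. Reference points side by side**

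| Item | Protocol 12.3 | SAP |
|---|---|---|
| Change in labs, ECG, vital signs | Entry Visit | Parent Baseline (9.3, 9.5.1, 9.5.2) |
| Change in weight | Entry Visit | Default is parent Baseline; 9.5.1 does not name weight, and 9.5.4.3 only lists physical-examination data |
| Lab, vital-sign and weight flags | Planned, no reference named | Depends on the rule (step 2) |
| ECG flags | Listing only | Parent Baseline for PR and QRS emergence and for the 60 ms rise (13.3) |
| Adverse events | Not at issue | First EP0093 dose (9.2) |

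**2. Which adult flags depend on Baseline**

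- *Dependent:* PR and QRS emergence and the QT/QTc rise of at least 60 ms (13.3); pulse, systolic and diastolic pressure, and weight (13.2); urinalysis shift of at least 2 degrees (13.1.3). The laboratory shift tables in 9.3 also start from Baseline.
- *Not dependent as written:* respiratory rate, ECG heart rate, and QT/QTc above 500 ms. Hematology and chemistry (13.1.1, 13.1.2) use fixed cut-offs or fractions of LLN/ULN. The appendix calls these criteria treatment-emergent but gives no rule for emergence.

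**3. The SAP rules applied to hypothetical values**

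Each row gives parent Baseline / Entry / EP0093 visit.

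| Rule | Values | Against parent Baseline | Against Entry |
|---|---|---|---|
| PR >200 ms, emergent | 195/205/205 | +10, flagged | 0, not flagged |
| QTcF rise ≥60 ms | 388/448/450 | +62, flagged | +2, not flagged |
| Pulse <50 with fall ≥15 | 70/49/49 | −21, flagged | 0, not flagged |
| Weight change ≥10% | 80/72/72 kg | −8/80 = −10%, flagged | 0%, not flagged |
| Urine grade shift ≥2 | 0/2/2 | +2, flagged | 0, not flagged |
| PR >200 ms, resolved then recurs | 205/195/205 | not flagged | +10, flagged |
| PR >200 ms throughout | 205/205/205 | not flagged | not flagged |

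The first five rows are carry-over. The sixth is a change within EP0093 that the SAP rule misses. The seventh shows that an abnormality already present at parent Baseline is not carried over.

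**4. What the entry criteria allow through**

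Protocol 6.2 excludes QTcB or QTcF above 450 ms and lists a PR interval of 220 ms or more among its ECG exclusions. It also excludes ALT, AST or ALP above 2xULN and raised total bilirubin. Large persisting abnormalities of these kinds should not enter. The carry-over cases for PR (205 ms at Entry) and QTcF (448 ms at Entry) fall below those limits. Section 6.2 sets no numerical limit for QRS, pulse, blood pressure, weight or urinalysis.

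**5. Size**

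The documents give no rates. As an assumption, let p be the share of subjects with a persisting abnormality that arose between parent Baseline and Entry, and q the share with a new one, with no overlap. Per 1000 subjects, the SAP count is 1000(p+q), the Entry-based count is 1000q, and the ratio is (p+q)/q.

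- p = 0.5%, q = 10%: 105 against 100, ratio 1.05
- p = 2%, q = 5%: 70 against 50, ratio 1.4
- p = 5%, q = 2%: 70 against 20, ratio 3.5

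These figures leave out the missed recurrences of step 3, which work in the opposite direction. The range shows only that the answer depends on rates nobody can read from the plan.

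**The case against.** **Parent Baseline is the better pre-drug reference.** It precedes any study medication. Entry falls at the end of the parent study's Conversion Period (Protocol 5.1), and some subjects had received up to 800 mg/day (Protocol 5.3). For them, change from Entry would hide effects already present. This stands, and it is why the parent-Baseline tables should stay. It does not explain why the protocol's summary disappears or why SAP 3.9 is silent. The amendment history in SAP 14.1 shows that the switch was deliberate, but gives no reason and does not identify it as a departure from the protocol.

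**The protocol does not set a reference for flags.** Correct. A reader might infer that the SAP contradicts the protocol on flags as well; the text supports a contradiction only for change summaries. A reader might also infer that every treatment-emergent flag is affected. Step 2 shows otherwise, and SAP 9.5.1 and 13.2 call the vital-sign criteria abnormal rather than treatment-emergent.

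**The outputs already allow some separation.** Observed values are summarised by visit, flags are shown by 3-month interval with subject numbers, listings include the parent data used, and AEs ongoing at entry are tabulated. This helps at group level and for case review. It does not tell a reader of the flag tables which subjects already met the criterion at Entry.

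**The primary safety variables are not involved.** Correct. They are TEAEs and TEAEs leading to withdrawal (Protocol 4.1.1). The measurements here are other safety variables (Protocol 4.1.2).

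**Conclusion.** Wrong as written, on a limited point: the SAP contradicts a protocol-defined analysis without listing the change. This rests on the texts alone and needs no assumption.

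It also follows from the rules that the Baseline-dependent flags can attribute a stable earlier change to EP0093, that the PR and QRS rule can miss a recurrence, and that treatment-emergent has two references. How often this happens is unknown. The ratios of 1.05 to 3.5 rest on assumed rates and are not estimates.

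Three stronger readings are not supported:

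- **That a particular number of subjects per 100 will be wrongly flagged.** The documents contain no incidence or persistence rates, and the entry exclusions limit carry-over of large liver-test, QTc and PR abnormalities.
- **That the same abnormality will be counted twice.** Neither document plans a pooled parent-plus-extension analysis.
- **That parent Baseline is the wrong reference.** It answers a different and legitimate question.

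All analyses are descriptive and no test is affected. The point should still be fixed, because long-term safety is the primary objective and these tables are open to misreading.

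**What to change.** 1. Keep the parent-Baseline tables and label them as change from the pre-drug reference.
2. Add the protocol-defined change from Entry Visit for laboratory values, ECG, vital signs and weight, and say where the weight summary will appear.
3. In the PCST and abnormality tables, separate subjects already meeting the criterion at Entry from those first meeting it after the first EP0093 dose. Show recurrences after a normal Entry value.
4. State the emergence reference for every flag, including hematology and chemistry, and say whether the Entry record can itself count as a post-Baseline EP0093 visit.
5. Add a row to SAP 3.9 recording the parent-Baseline choice and its reason.

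The cost is SAP wording and some extra columns. No new data are needed: the Entry values for these measurements already come from the last parent-study visit (Protocol 8.1.1 and Table 5-1).
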